6.3.7 AVIVO / HealthPatch monitoring

AVIVO Mobile Patient Management System and HealthPatch is intended to continuously measure, record and periodically transmit ECG data.

Notifiable ECG-findings (like AV-conduction abnormalities) triggered by system/patients based, as well as reportable ECG finding according to AVIVO will be summarized in frequency tables by treatment group. ECG-findings according to HealthPatch will also be summarized in frequency tables by treatment group. A table displaying the number of patients with AV block $> 1^\circ$ according to AVIVO/HealthPatch will be provided by treatment group. All patients with significant ECG-finding will be listed. The definition of the findings that trigger a notifiable report is in Appendices 9.1.

6.3.8 Other safety measures

The last pre-treatment safety measurement, i.e. SBP (systolic blood pressure), DBP (diastolic blood pressure), weight, body temperature, heart rate, respiration rate and electrocardiogram (12 lead ECG) will be used as “baseline value.”

When more than one value is collected at the same post-baseline visit, the value retained at that particular visit for summary statistics will be the average of the different measures reported for that visit.

For each treatment group, vital signs will be tabulated and summarized by visit for observed values and changes from baseline using descriptive statistics, as appropriate. Summary statistics and figures of heart rate and blood pressure (systolic, diastolic, and mean arterial pressure) will be created.

The incidence rates of treatment-emergent 12-lead ECG abnormalities will be tabulated by treatment group. A descriptive analysis of continuous ECG parameters and their changes from baseline by visit and treatment group will also be presented. PR interval will be summarized by visit and treatment group.

6.4 Subgroup Analysis

6.4.1 Subgroups

Subgroup variables are specified in Section 4.5.4.

6.4.2 Subgroup analysis of efficacy variables

Primary and secondary analyses of primary efficacy variable will be performed based on key subgroups. Additionally primary efficacy variable will be descriptively summarized based on exploratory subgroups.

Secondary efficacy variables will be descriptively summarized based on key subgroups.

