3.3 Neladenoson bialanate

Neladenoson bialanate (BAY 1067197, which is the free base of the hydrochloride BAY 86-8901) is the pro-drug of the pharmacologically active compound BAY 84-3174, a highly potent and selective non-adenosine like partial adenosine A1 receptor agonist suitable for once daily oral use.

Pharmacological actions seem to be at least partly based on an acute restoration and improved utilization of myocyte energetics (ATP production within the mitochondria), and chronic improvement of calcium handling by restoration of SERCA2a protein levels, which result in protection of cardiac function and improvement of contraction / relaxation coupling. These effects were seen after a short treatment period of one week in nonclinical models. In addition, neladenoson bialanate was characterized regarding mitochondrial function in isolated cardiomyocytes from normal and HF dogs (EF $\sim\!\!30\%$) produced by intracoronary microembolization as described in Sabbah et al (77). Neladenoson bialanate improved mitochondrial function (respiration, ATP synthesis, ATP / adenosine diphosphate [ADP] ratio, cytochrome c-dependent cyclooxygenase activity, membrane potential, and mitochondrial permeability transition pore opening) significantly and dose dependently in HF cardiomyocytes but had no effect on normal cardiomyocytes. Since both impaired myocardial energetics and disturbed calcium reuptake are considered key contributors to the pathophysiology of HFpEF, neladenoson bialanate has the potential to be a suitable treatment option for HFpEF patients to improve symptomatic status, morbidity and survival.

Furthermore, up to 80% of HFpEF patients are on a β-blocker to optimize treatment of comorbidities, such as CAD or hypertension (29). However, β-blockers can exacerbate chronotropic incompetence, an important cause of exercise intolerance in patients with HFpEF found in 50-80% of patients (23, 78, 79). Other than β-blockers, neladenoson

14 FEB 2017 Version: 1.0 Page: 21 of 85

bialanate shows no effects on heart rate in preclinical (39) and clinical models (49). Thus, it is a suitable option in patients with HFpEF, where a treatment not damping heart rate would be desirable.

Nonclinical data showed that neladenoson bialanate is cardio- and renoprotective at doses lower than needed to elicit the clinically relevant undesirable effects on heart rate, AV-conduction, blood pressure, renal function and the central nervous system.

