10.3.2 Statistical and analytical plans

All data will be listed and all variables will be summarized by means of descriptive statistics according to their type.

Summaries by treatment group using appropriate descriptive statistics will be provided for all study variables including demographic and baseline characteristics. Summary statistics will be presented for the original data as well as for the difference to baseline. Descriptive statistics such as mean, median, standard deviation, quantiles, minimum, and maximum will be used to summarize continuous variables. Counts and percentages will be used to summarize categorical variables. Life tables and Kaplan-Meier estimates will be used to summarize time-to-event variables. Graphical data displays may also be used to summarize the data. Confidence intervals will be provided at a 2-sided level of 90% unless otherwise stated.

For this combined proof-of-concept and dose-finding study, an overall one-sided type I error level of 5% is planned to be used. The type I error will be controlled for the primary analysis of the primary variable.

There will be no formal control of the type I error for secondary or explorative analyses of the primary variables and any analysis of other efficacy variables.

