10.3.2.2 Analysis of the primary efficacy variable

It is planned to perform a test for a dose-response signal under the assumption of a nearly monotone dose-response relationship in the dose range considered. The MCP-Mod method (84) combining multiple comparison procedures (MCP) principles with modeling techniques will be used for the primary statistical analysis of the primary efficacy variable. This method allows the flexibility of modeling for dose estimation, while preserving the robustness to model misspecification associated with MCP procedures.

14 FEB 2017 Version: 1.0 Page: 60 of 85

Assumptions

Five active doses of neladenoson bialanate will be used in this study: 5 mg, 10 mg, 20 mg, 30 mg, and 40 mg, as well as a placebo arm corresponding to a 0 mg dose.

The measurements of the primary efficacy variable are assumed to be normally distributed with the same standard deviation σ and independent between patients.

The following assumptions were made for the absolute change from baseline in 6MWD over 20 weeks:

- the expected mean effect under the placebo dose is assumed as an absolute difference from baseline of $\Lambda = 0$ m with a standard deviation of $\sigma = 80$ m
- while the maximum observable mean effect under neladenoson bialanate within the dose range considered is assumed as an absolute increase of $\Delta = 40$ m with a standard deviation of $\sigma = 80$ m.

This results in an expected maximum effect size of (40-0)/80 = 0.5.

It is assumed that the primary efficacy variable, denoted as Y, is observed for the 6 parallel groups corresponding to doses levels: (placebo =) $d_1 < d_2 < ... < d_k$, where k = 6.

For patient *j* within treatment group *i* the response can then be described by the following model:

$$Y_{ij} = f(d, \mathbf{\theta}) + \varepsilon_{ij}, \quad \varepsilon_{ij} \sim N(0, \sigma^2), \quad i = 1, ..., k, j = 1, ..., n_i,$$

where f(.) is parameterized by a vector of parameters θ and ε_{ij} is the error term.

A candidate set with M=5 different dose response shapes f(.) based on four models was chosen for the MCP-Mod method. Table 10—1 displays the response expressions for the shapes in the candidate set. Figure 10—1 shows the corresponding dose-response shapes. The model parameters were obtained through discussions with experts in the clinical team, taking prior beliefs and uncertainty into account.

Table 10—1: Dose-response shapes used in the candidate set

Model	Response as function of dose d
Linear	d

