10.4 Determination of sample size

This combined proof-of-concept and Phase IIb dose-finding study has been powered for the detection of a dose response signal in the primary efficacy variable.

The sample size for the primary efficacy variable was evaluated under the assumptions described in Section 10.3.2.2 and a type I error level = 5% with the aim to achieve at least 80% power for the one-sided primary multiple contrast test. The overall randomization ratio was assumed to be 3:1:2:2:2:2 for doses 0, 5, 10, 20, 30, and 40 mg.

Table 10—2 displays the power for the multiple contrast test in the MCP-Mod approach, used as primary analysis, for the set of specified alternatives.

Table 10—2: Power for multiple contrast test for set of different alternatives									
Sam	ple size	Pow	er for alternative	e bas	sed on respectiv	e do	se-res	ponse model (i	in %)
(oroll	Dor group a	Lincor	Ciampidal E	4	Ciamoidal E	2	_	Oundratia	Mini

Sample size			Power for alternative based on respective dose-response model (in %)						
O	verall	Per group ^a	Linear	Sigmoidal E _{max} 1	Sigmoidal E _{max} 2	\mathbf{E}_{max}	Quadratic	Minimum	
-	180	30	74.10	86.84	81.84	82.96	80.59	74.10	
	192	32	76.54	88.75	84.07	85.11	82.82	76.54	
:	204	34	78.83	90.39	86.05	87.04	84.86	78.83	
	216	36	80.84	91.81	87.80	88.72	86.61	80.84	
:	228	38	82.76	93.03	89.36	90.23	88.23	82.76	
:	240	40	84.48	94.05	90.73	91.51	89.62	84.48	
:	252	42	86.06	94.97	91.92	92.67	90.88	86.06	
:	264	44	87.45	95.72	92.96	93.65	91.96	87.45	

a Number of patients randomized to dose levels 10 mg, 20 mg, 30 mg, and 40 mg of neladenoson bialanate, for placebo sample size per group to be multiplied by 3/2, for dose level 5.0 mg sample size per group to be divided by 2.

To achieve at least 80% power for the multiple contrast test in the MCP-Mod approach under all different alternatives, a minimum of 36 patients per treatment group (54 patients for the placebo and 18 patients for the 5 mg group) is needed, resulting in an overall sample size of 216 patients.

Based on this estimation, a total of 288 patients are planned to be randomized to the 6 treatment groups:

- 72 patients are planned to be randomized to placebo (0 mg),
- 48 patients each are planned to be randomized to the dose levels 10 mg, 20 mg, 30 mg, and 40 mg of neladenoson bialanate, and
- 24 patients are planned to be randomized to the dose level 5 mg of neladenoson bialanate.

14 FEB 2017 Version: 1.0 Page: 67 of 85

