4.5.4 Subgroup Analyses

In order to assess the homogeneity of the dose response across the most important prognostic and predictive factors, subgroup analyses will be performed.

‘Key’ subgroups include:

- LVEF (%) at baseline: <55 vs. ≥ 55

Statistical Analysis Plan

Protocol No.: < BAY 1067197/17582>

Page: 13 of 38

- NT-proBNP (pg/mL) at baseline: ≤ median vs. > median
- NYHA class at baseline: II vs. III / IV
- Prior β-blocker: yes vs. no

All other exploratory subgroups comprise demographic and baseline characteristics specified in Section 6.1.2.

If the total number of patients in a subgroup category is too small, the respective subgroup category will be either omitted from the analysis or combined with other categories, if a logical combination to another subgroup category is possible.

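### The key-subgroup analyses aim to assess homogeneity of the dose response, but the plan neither estimates nor tests a difference between subgroup levels

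*SAP*

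**What the plan says.** The aim is stated in Protocol 10.3.2.1 and again in SAP 4.5.4: "In order to assess the homogeneity of the dose response across the most important prognostic and predictive factors, subgroup analyses will be performed". Four two-level key factors follow: LVEF (below 55% or not), NT-proBNP (split at the median), NYHA class (II or III/IV) and prior β-blocker (yes or no).

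The inferential method is in SAP 6.4.2: "Primary and secondary analyses of primary efficacy variable will be performed based on key subgroups". The primary analysis (SAP 6.2.1.2) is the MCP-Mod multiple contrast test, which ends in signal or no signal. The secondary analysis (SAP 6.2.1.3) is an unadjusted 90% confidence interval for each dose minus placebo. Protocol 10.3.2.2 also has dose-response curves fitted in relevant subgroups.

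Neither document contains a dose-by-subgroup term, a difference of contrasts between levels, or a heterogeneity test. The adjusted analysis in SAP 6.2.1.5 uses only baseline 6MWD, age and gender as covariates.

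**The concern.** Homogeneity is a statement about the difference between levels, and that difference is the one quantity the plan does not produce. The output for the key factors will include up to eight by-level test results, each on a fraction of a sample sized for about 80% power as a whole. When power per level is near one half, two levels with the same true effect will often fall on opposite sides of the critical value. A reader of that table may take the split as effect modification.

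This matters because Protocol section 4 says the sponsor will weigh the totality of the data, including secondary and exploratory endpoints, in deciding whether to move to Phase III.

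**Working it through.** **Inputs.** From Protocol 10.3.2: "an overall one-sided type I error level of 5% is planned to be used". From 10.3.2.2: "A candidate set with M=5 different dose response shapes", and "This results in an expected maximum effect size of" (40 − 0)/80 = 0.5. From 10.4: "The overall randomization ratio was assumed to be 3:1:2:2:2:2 for doses 0, 5, 10, 20, 30, and 40 mg", so that 216 evaluable patients are 54/18/36/36/36/36, "with the aim to achieve at least 80% power for the one-sided primary multiple contrast test". Subgroup sizes are not in the documents, apart from the NT-proBNP median split; all other splits are assumptions.

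**Step 1: reproduce the plan's power.** With optimal contrasts proportional to n_i(μ_i − μ̄), the non-centrality of the matching contrast is √[Σ n_i(μ_i − μ̄)²]/σ.

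- Linear: μ̄ = 3,690/216 = 17.08; Σ n_i(μ_i − μ̄)² = 108,450 − 3,690²/216 = 45,412.5; non-centrality = 213.1/80 = 2.66.
- The largest of the five contrasts is referred to the multivariate t critical value, about 1.97.

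| Shape | Table 10-2 at N = 216 | Reproduced |
|---|---|---|
| Linear | 80.84% | 80.9% |
| Sigmoidal Emax 1 | 91.81% | 91.8% |
| Sigmoidal Emax 2 | 87.80% | 87.7% |
| Emax | 88.72% | 88.7% |
| Quadratic | 86.61% | 87.3% (86.8% if scaled to a 40 m maximum) |

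**Step 2: power within a level.** Halving every n divides the non-centrality by √2: for the linear shape 2.66/√2 = 1.88, below the critical value of about 1.98. Power in a half-sized level (N = 108) is about 54–69% across the shapes; in a quarter-sized level (N = 54) it is about 33–43%.

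**Step 3: one factor, same effect in both levels.** The levels hold different patients, so for an even split with power p in each, P(significant in one level only) = 2p(1 − p).

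- p = 0.55: 2 × 0.55 × 0.45 = 0.495.
- p = 0.69: 2 × 0.69 × 0.31 = 0.428.

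Simulation agrees: about 43–50%, rising to about 60% for an 80:20 split.

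**Step 4: at least one of four factors.** Treating the factors as independent would give 1 − (1 − 0.43)⁴ = 89% to 1 − (1 − 0.50)⁴ = 94%. That is too high, because all four factors divide the same outcome data. Simulating whole trials (216 patients, SD 80 m, same dose response in every patient) gave:

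| Scenario | At least one factor significant in one level only |
|---|---|
| Full effect, four 50:50 splits | 73–81% |
| Full effect, splits 40/50/60/75% | 81–86% |
| Full effect, splits 30/50/70/80% | 86–89% |

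Simulation error is about 1 point, up to 2.5 in the smaller runs. Over all runs the ranges are about 72–89% at the full effect, 60–71% at half the effect and 20–28% at no effect. A latent correlation of 0.3 between factors changed little.

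**Step 5: a direct between-level comparison.** A dose-by-subgroup max-|T| test at two-sided 5%, under the same full effect in everyone and even splits, is falsely positive in 4–5% of trials per factor and in 17–19% for at least one of four (1 − 0.95⁴ = 18.5%). At 10% the latter would be 1 − 0.9⁴ = 34% if the tests were independent.

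Power is low. With even halves, the standard error of the between-level difference is twice that of the overall contrast. If the full effect exists in only one half, the linear non-centrality is therefore 2.66/2 = 1.33, against a critical value of about 2.27. Simulated power was 23% (linear) to 31% (sigmoidal Emax 1).

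**The case against.** The strongest reply is that these analyses are exploratory. Protocol 10.3.2 disclaims type I error control outside the primary analysis, and nothing in the trial's main conclusion depends on them. That stands. It excuses the absence of multiplicity control, but not the absence of the comparison the analyses are meant to make.

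Four stronger readings are tempting, and the documents do not support them:

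- **That more than 80% of trials would show a false subgroup difference.** The figure depends on conditions. With even splits, four of the five shapes give 73–79% at the full effect, and the rate falls well below that at smaller effects. It also counts any of four factors, and neither document says that discordant significance will be called a difference.
- **That the plan cannot assess homogeneity at all.** By-level 90% intervals and fitted curves allow a descriptive comparison. What is missing is an estimate of the difference, with its uncertainty.
- **That β-blocker use will split 80:20.** Protocol 3.3 says "up to 80% of HFpEF patients are on a β-blocker". This is an upper figure for HFpEF patients in general, and SAP 6.1.4 defines prior medications as those stopped before first dose. The 80:20 split is therefore only one scenario.
- **That a Phase III population will be picked from these subgroups.** The documents speak of the dose and the decision to proceed.

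Sparse levels are partly covered: SAP 4.5.4 allows a category that is too small to be omitted or combined.

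**Conclusion.** The point holds as a mismatch between aim and method. The plan sets out to assess homogeneity and specifies only repeats of the analysis by level; reading SAP 6.4.2 as separate analyses in each level is natural, though not spelled out. If by-level significance is used to judge homogeneity, it will mislead often: about 43–50% of trials for one evenly split factor and about 72–89% for at least one of four, when the effect is the same in everyone. On the same any-of-four count, interaction tests at 5% give 17–19%.

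These figures rest on the design SD, the full 40 m effect, 216 evaluable patients and assumed subgroup sizes. The primary analysis is not affected. The change is worth making because it uses data already collected.

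**What to change.** In SAP 6.4.2, keep the by-level analyses and add, for each of the four key factors:

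1. One model on the full per-protocol set with dose group, subgroup and dose group × subgroup, and a pooled SD.
2. Each candidate contrast by level, and the difference between levels with a 90% confidence interval.
3. Optionally, a max-|T| interaction test, labelled exploratory and unadjusted across the four factors.
4. A sentence that by-level signal or no-signal results will not be read as evidence for or against homogeneity.

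The by-level tests should stay, because the contrast test is the gate to Step 2 in SAP 6.2.1.2 and Protocol 10.3.2.2 commits to subgroup modelling.

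The cost is a short SAP addition and one model per factor. The drawback is the imprecision shown in Step 5: low power for a real interaction, and an appreciable chance of at least one false positive across four tests. Estimates and intervals should lead the report, and it should say that a non-significant interaction does not establish homogeneity.

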6.4.3 Subgroup analysis of safety variables

Incidence rate of treatment-emergent AEs and treatment-emergent ECG abnormalities not present at baseline (by AVIVO and HealthPatch, Japan only) will be summarized based on key and exploratory subgroups.

Statistical Analysis Plan

Protocol No.: < BAY 1067197/17582 >

Page: 29 of 38

6.5 Pharmacokinetics/pharmacodynamics

Pharmacokinetic analyses will be performed on the population valid for pharmacokinetics.

For the investigation of systemic exposure to BAY 84-3174 and its relationship with treatment effects, the plasma concentrations of BAY 84-3174 will be determined at different time points using a sparse sampling approach in all participating patients (see Section 9.5 of Clinical Study Protocol). The plasma concentration vs. time data will be evaluated descriptively separated by dose and visit. Plots will be prepared pooling all individual plasma concentrations (naive pooling) vs. actual relative study times (time of sample collection after time of study drug administration).

Furthermore, the pharmacokinetic data and the relationship of markers of BAY 84-3174 exposure (e.g. Cmax, AUC) with treatment effects will be evaluated using non-linear mixed effect modeling (NONMEM). The latter evaluation will be described in a separate analysis plan and will be reported under separate cover.

The PK bioanalysis will be performed under the responsibility of the Sponsor's Bioanalytics Laboratory.

6.6 Biomarker analyses

Biomarker data will be described by treatment group by the following summary statistics: arithmetic mean, standard deviation, median, quantiles, minimum, and maximum.

Box plots and line plots of means of biomarkers over visits, by treatment group will be provided.

Additional analyses of safety and efficacy biomarkers and their results will be provided in a separate report.

7. Document history and changes in the planned statistical analysis

List major milestones of the SAP development including the dates they have been reached, e.g.:

- Approval of the SAP, dated 15 DEC 2017.
- Approval of the SAP version 2, dated 15 JUN 2018.

8. References

3. R Core Team (2017). R: A language and environment for statistical computing. R Foundation for Statistical Computing, Vienna, Austria. URL <https://www.R-project.org/>.

Statistical Analysis Plan

4. Bjoern Bornkamp, Jose Pinheiro and Frank Bretz (2016). DoseFinding: Planning and Analyzing Dose Finding Experiments. R package version 0.9-15. <https://CRAN.R-project.org/package=DoseFinding>.
6. Rubin DB. Multiple imputation for nonresponse in surveys. New York: Wiley; 1987.
7. The Kansas City Cardiomyopathy Questionnaire Scoring Instructions (2000-2003), John Spertus MD MPH [<http://cvoutcomes.org/> (6th September 2013)].
8. C. Patrick G, et al. Development and Evaluation of the Kansas City Cardiomyopathy Questionnaire: A New Health Status Measure for Heart Failure, Journal of the American College of Cardiology, 2000; 35(5):1245-55.

9. Appendices

9.1 AVIVO device variable specification

In the following, we describe the variables which will be analyzed.

- **Activity**

Variable	Summary measure(s)	Unit	Length of intervals
activity duration	duration	seconds	1 hour
activity intensity	mean	mG	1 hour
activity intensity	mean, max	%	daily

- **Abnormal findings that trigger a notifiable report are defined as below**

Finding	Notification criteria
Ventricular fibrillation	always notified
ICD discharge	always notified
Ventricular Tachycardia	any rate and ≥ 10 beats
Wide complex Tachycardia	any rate and ≥ 10 beats
PVCs	never notified
Sinus Bradycardia	≤ 30 bpm
Sinus Tachycardia	≥ 180 bpm
Supraventricular tachycardia	≥ 150 bpm AND ≥ 30 sec
A. Fibrillation or A. flutter	≥ 150 bpm AND ≥ 30 sec
A. Fibrillation or A. flutter	≤ 30 bpm and ≥ 30 sec

Statistical Analysis Plan

Protocol No.: < BAY 1067197/17582 >

Page: 31 of 38

A. Fibrillation or A. flutter	when notification criteria are met
Pause	≥ 3.0 sec
AV block 2nd (Mobitz I)	≤ 50 bpm
AV block 2nd (Mobitz II)	always notified
Isolated 2nd degree AV block (2:1)	≤ 50 bpm
High degree AV block	always notified
3rd Degree AV block	always notified
Other	
Patient triggered Events	when notification criteria are met
Technicians discretion	any

